# **Table 3** Vital Signs – Dose Escalation Part

Notes	Section Reference	Time Point
	9.3.3	Pre-infusion (up to 30 min before infusion)
		15 min after start of infusion (±5 min)
If infusion lasts for more than 60 minutes, vital signs should be assessed every 15 minutes (± 5 minutes) for the remaining duration of the infusion		At the end of infusion (±5 min)
		30 min after end of infusion (±5 min)
	·	1 hour after end of infusion (±10 min)
		2 hours after end of infusion (±10 min)

 Table 4
 Biomarker Table – Dose Escalation Part

[figure not shown]

 Table 4
 Biomarker Table – Dose Escalation Part (Continued)

Document Number: TMF-34513

 Table 5
 Visit Evaluation Schedule – Expansion Part

Treatment Cycle (C)	Notes	Section Reference	Screening					Сус	le 1							Cycle	2		
Day (d)/Week (wk)			≤28d prior to C1 (1d)	1d	2d	4d	8d	9d	11d	15d	16d	18d	1d	2d	4d	8d	9d	11d	15d
Visit window							+1d			+1d			+2d			+2d			+2d
Informed Consent		13.2.3	X																
Eligibility Criteria		5.1, 5.2, 9.4.2	X																
Demographics		9.1.1	X																 
Medical History		9.1.2 to 9.1.5	X																
Body weight		9.3.2	X																
Physical Examination	Full physical exam at Screening. After Screening, perform exam only as indicated by subject's symptoms, AEs, or findings as determined by investigator.	9.3.1	X	X			X			X			X						X
Vital Signs	Full vital signs only at Screening; for subsequent visits, only temperature and blood pressure. See Table 7 for GEN1044 dosing days. At Unscheduled visit, perform only as indicated by subject's symptoms, AEs, or findings as determined by investigator.	9.3.3	X	X			X			X			Х						X
ICE Score Assessment	See Table 18.	10.4.2	X	X			X			X			X						
ECG	See Table 6	9.3.4	X																
Radiological Exam/Tumor Imaging	See footnote "a" regarding Screening. Imaging is calendar based. On-treatment imaging every 6 wks (±7d) for the first 36 wks (calculated from C1D1), then every 12 wks (±7d) until PD, start of new anticancer therapy, consent withdrawn, or death, whichever occurs first.	9.2.1	Xª																
Whole-body Bone Scan	Subjects with prostate cancer. Ontreatment scans every 6 wks (±7d) for the first 24 wks (calculated from C1D1), then every 12 wks (±7d) until PD, start of new anti-cancer therapy, consent withdrawn, or death, whichever occurs first.	9.2.1	X																

Document Number: TMF-34513

Treatment Cycle (C)	Notes	Section Reference	Screening					Cyc	le 1							Cycle	2		
Day (d)/Week (wk)			≤28d prior to C1 (1d)	1d	2d	4d	8d	9d	11d	15d	16d	18d	1d	2d	4d	8d	9d	11d	15d
Visit window							+1d			+1d			+2d			+2d			+2d
ECOG-PS	Do not perform C1D1 ECOG-PS if within 5 days of Screening ECOG-PS. C1D1 ECOG-PS must be within 0-1 or subject cannot receive GEN1044. At Unscheduled visit, only if relevant.	9.3.5	X	X									X						
Adverse Events	See footnote "b." Report all AEs from first GEN1044 dose (C1D1) until 30 days after the last GEN1044 dose (ie, Safety Follow-up Visit). After SFU only report suspected GEN1044-related SAEs.	10.1, 10.2	X	X	X	X	X	X	X	X	X	X	X	X	X	X		X	X
Concomitant Medication		6.5, 9.1.4	X	X	X	X	X	X	X	X	X	X	X	X	X	X		X	X
Premedication with Corticosteroids, Antihistamines and Antipyretics	Premedication is mandatory 30 to 120 minutes prior to first 3 administrations of GEN1044	6.2, 6.5		X			X			X									
GEN1044 Administration f		6.3, 6.6		X			X			X			X			X			X
LABORATORY ASS	SESSMENTS																		
Hematology	At Unscheduled visit, only if relevant.	9.4	X c	X	X	X	X	X	X	X	X	X	X			X			X
Biochemistry	At Unscheduled visit, only if relevant.	9.4	X c	X	X	X	X	X	X	X	X	X	X		X	X		X	X
Coagulation factors	At Unscheduled visit, only if relevant.	9.4	Xc	X									X						
Urinalysis	At Unscheduled visit, only if relevant.	9.4	X c																
Pregnancy test	At Unscheduled visit, only if relevant.	9.4	Xc																
Hepatitis B	At Unscheduled visit, only if relevant.	9.4	Xc																
T3, T4	At Unscheduled visit, only if relevant.	9.4	X c																
PK/ADA sampling	See Table 6	9.5, 9.6																	
Tumor biopsy, biomarkers	See Table 8	9.7	X																
PSA	Subjects with prostate cancer; central lab	9.2.2	X c	X									X						
Serum testosterone	Subjects with prostate cancer; central lab	9.4.1	Xc																

Document Number: TMF-34513

 Table 5
 Visit Evaluation Schedule - Expansion Part (Continued)

Treatment Cycle (C)	Notes	Section Reference		Sycle 3 Cycle 4		Сус	cle 5 to	) PD	Treatment Discontin- uation visit	Safety Follow-up visit	Survival Follow-up	Unsched- uled
Day (d)/ Week (wk)			1d	8d	15d	1d	8d	15d	-	30d after last dose	Every 12 wk after last dose	
Visit window			+3d	+3d	+3d	+3d	+3d	+3d		+14d	+7d	
Body weight		9.3.2							X			
Physical Examination	Full physical exam at Screening. After Screening, perform exam only as indicated by subject's symptoms, AEs, or findings as determined by investigator.	9.3.1	X	X	X	X			X	X		X
Vital Signs	See Table 7 for GEN1044 dosing days. At Unscheduled visit, perform only as indicated by subject's symptoms, AEs, or findings as determined by investigator.	9.3.3	X	X	X	X			X	X		X
ECG	See Table 6	9.3.4										
Radiological Exam/Tumor Imaging	Imaging is calendar based. On-treatment imaging every 6 wks (±7d) for the first 36 wks (calculated from C1D1), then every 12 wks (±7d) until PD, start of new anti-cancer therapy, consent withdrawn, or death, whichever occurs first.	9.2.1							X d			
Whole-body Bone Scan	Subjects with prostate cancer. On-treatment scans every 6 wks (+7d) for the first 24 wks (calculated from C1D1), then every 12 wks (±7d) until PD, start of new anti-cancer therapy, consent withdrawn, or death, whichever occurs first.	9.2.1							X d			
ECOG-PS	At Unscheduled visit, only if relevant.	9.3.5	X			X			X	X		X
Adverse Events	See footnote "b." Report all AEs from first GEN1044 dose (C1D1) until 30 days after the last GEN1044 dose (ie, Safety Follow-up Visit). After SFU, only report suspected GEN1044-related SAEs.	10.1, 10.2	X	X	X	X			X	Х	X	Х
Concomitant Medication		6.5, 9.1.4	X	X	X	X			X	X		X
Premedication with Corticosteroids, Antihistamines and Antipyretics	Premedication is mandatory 30 to 120 minutes prior to first 3 administrations of GEN1044.	6.2, 6.5										
GEN1044 Administration		6.3, 6.6	X	X	X	X						
End of treatment	Perform Treatment Discontinuation visit as soon as possible after permanent GEN1044 discontinuation.	8.1, 8.1.1							X			

Document Number: TMF-34513

Treatment Cycle (C)	Notes	Section Reference		ycle 3 Cycle 4		Сус	ele 5 to	PD	Treatment Discontin- uation visit	Safety Follow-up visit	Survival Follow-up	Unsched- uled
Day (d)/ Week (wk)			1d	8d	15d	1d	8d	15d	-	30d after last dose	Every 12 wk after last dose	
Visit window			+3d	+3d	+3d	+3d	+3d	+3d		+14d	+7 d	
Inquire if any new												
anti-cancer		8.1.2							X	X	X	
treatment												
Survival follow-up	Perform survival follow-up by telephone, email, or visit.	9.2.3									X	
LABORATORY AS	SSESSMENTS											
Hematology	At Unscheduled visit, only if relevant.	9.4	Xe			Xe			Xe	X		X
Biochemistry	At Unscheduled visit, only if relevant.	9.4	Xe			Xe			Xe	X		X
Coagulation factors	At Unscheduled visit, only if relevant.	9.4							Xe			X
Urinalysis	At Unscheduled visit, only if relevant.	9.4	Xe			Xe			Xe			X
Pregnancy test	At Unscheduled visit, only if relevant.	9.4	Xe			Xe			Xe			X
Hepatitis B	At Unscheduled visit, only if relevant.	9.4										X
T3, T4	At Unscheduled visit, only if relevant.	9.4										X
PK/ADA sampling	See Table 6	9.5, 9.6										
Tumor biopsy, biomarkers	See Table 8	9.7				_						
PSA	Subjects with prostate cancer; central lab	9.2.2	Xe			X			X			X
Serum testosterone	Subjects with prostate cancer; central lab	9.4.1										

- a. During Screening: All subjects will have a contrast CT of the chest/abdomen/pelvis; a non-contrast CT of chest and MRI of abdomen/pelvis, or chest x-ray as applicable for their respective tumor type. For subjects with SCCHN, head and neck imaging is also required; imaging of the pelvis is strongly recommended but not required. If a CT-scan or MRI has been performed within 28 days prior to visit Cycle 1 Day 1 as part of standard procedure, it is acceptable as a screening scan for the trial. If there is suggestion of brain metastases/tumors, a CT-scan or MRI of the head and neck will be performed within 28 days prior to the Cycle 1 Day 1 visit. A bone scan is required for subjects with prostate cancer.
- b. Medical conditions occurring after ICF is signed and prior to first GEN1044 dose should only be reported as AEs if they were assessed by the investigator to be caused by a protocol-mandated procedure (ie, tumor biopsy and/or CT scan), including washout or discontinuation of prior medications. Any medical history that worsens after the first dose of GEN1044 will be recorded as an AE. If the subject initiates new anti-cancer therapy within 30 days of the last dose of GEN1044, the SFU visit should be performed prior to starting new anti-cancer therapy. SAEs still ongoing after Safety Follow-up visit should be followed on a regular basis according to the investigator's clinical judgment until the event has been resolved or until the investigator assesses it as chronic and all queries have been resolved.
- c. Obtain screening labs within 7 days of Cycle 1 Day 1 (exception: hepatitis B sample may be obtained earlier). Central lab: serum (beta-hCG) pregnancy, hepatitis B, T3, T4, serum testosterone, PSA; local lab: hematology, biochemistry, coagulation factors and urinalysis.
- d. Radiological exam/tumor imaging and if applicable, bone scan, at Treatment Discontinuation visit unless performed within 28 days of last scheduled exam.
- e. Starting with C3, obtain labs ≤3 days before D1. Central lab: PSA; local lab: hematology, biochemistry, coagulation factors, urine pregnancy test, and urinalysis.
- f. Subjects in cohorts receiving 1 interim dose will receive: A priming dose on C1D1; an intermediate dose on C1D8; and the first full dose on C1D15. Subjects in cohorts receiving 2 interim doses will receive: A priming dose on C1D1; intermediate doses on C1D8 and C1D15; and the first full dose on C2D1.

Document Number: TMF-34513

Version: 4.0

# Table 6 PK, ADA and ECG Sampling – Expansion Part

Treatment Cycle (C)	Notes	Section Reference	Screening	Cycle 1							Cycle 2								
Day (d)/Week (wk)			≤ 28d prior to C1 (1d)	1d	2d	4d	8d	9d	11d	15d	16d	18d	1d	2d	4d	8d	9d	11d	15d
Visit window							+1d			+1d			+2d			+2d			+2d
PK SAMPLING		9.5																	
Before Infusion (on infusion days)				X			X			X			X			X			X
End of infusion (+15 min)				X			X			X			X			X			X
24 hr sample after end of infusion	Collect C1D2 and C1D9 PK sample 24 hr ±2 hr after end of D1 and D8 infusion, respectively.				X			X											
ADA SAMPLING		9.6																	
Before Infusion (on infusion days)				Х									X						
ECGs		9.3.4																	
Before Infusion (on infusion days)	Single ECG		X																

Document Number: TMF-34513

Table 6 PK, ADA and ECG Sampling - Expansion Part (Continued)

Treatment Cycle (C)	Notes	Section Reference	Cycle 3 to Cycle 4 Cycle 5 to PD			Treatment Discontin- uation visit	Safety Follow-up visit	Survival Follow-up	Unscheduled			
Day (d)/ Week (wk)			1d	8d	15d	1d	8d	15d	-	30d after last dose	Every 12 wk after last dose	
Visit window			+3d	+3d	+3d	+3d	+3d	+3d		+14d	+7 d	
PK SAMPLING		9.5										
Before Infusion (on infusion days)	Optional at Unscheduled visits		Xª			Xª			X	X		X
End of infusion (+15 min)			Xa			Xa						
ADA SAMPLING		9.6										
Before Infusion (on infusion days)	Optional at Unscheduled visits		Xa			Xª			X	X		X
ECGs		9.3.4										
Before Infusion (on infusion days)	Optional at Unscheduled visits; single ECG if performed								X			X

a. Collect PK and ADA samples at C3D1, C5D1, C7D1, then every 4 cycles thereafter on Day 1.

Version: 4.0

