- $e. \ Starting \ with \ C3, obtain \ labs \leq 3 \ days \ before \ D1. \ Central \ lab: \ PSA; \ local \ lab: \ hematology, \ biochemistry, \ coagulation \ factors, \ urine \ pregnancy \ test, \ and \ urinalysis.$
- f. Only collect during C5.

Document Number: TMF-34513

 Table 2
 PK, ADA and ECG Sampling – Dose Escalation Part

Treatment Cycle (C)	Notes	Section Reference	Screening					Cycle	1							Cycle	2		
Day (d)/Week (wk)			≤ 28d prior to C1 (1d)	1d	2d	4d	8d	9d	11d	15d	16d	18d	1d	2d	4d	8d	9d	11d	15d
Visit window							+1d			+1d			+2d			+2d			+2d
PK SAMPLING		9.5																	
Before Infusion (on infusion days)				X			X			X			X			X			X
End of infusion (+15 min)				X			X			X			X			X			X
End of infusion +2 hr (±15 min)										X			X						
End of infusion +6 hr (+3 hr)				X			X			X			X						
24 hr sample post end of infusion	Collect C1D2, C1D9, and C1D16 PK sample 24 ±2 hr after end of D1, D8 and D15 infusion, respectively. Collect C2D2 sample 24 ±2 hr after the end of C2D1 infusion.				X			X			X			X					
72 hr sample post end of infusion	Collect C1D4 and C1D18 PK sample 72 ±24 hr after end of D1 and D15 infusion, respectively. Collect C2D4 sample 72 ±24 hr after the end of C2D1 infusion.					X						X			X				
ADA SAMPLING		9.6																	
Before Infusion (on infusion days)				X									X						
ECGs		9.3.4																	
Before Infusion (on infusion days)	Triplicate ECGs, performed within 20 minutes but at least 2 min apart		X	X			X												
End of infusion (+15 min)	Triplicate ECGs, performed within 20 minutes but at least 2 min apart			X			X												

Document Number: TMF-34513

Table 2 PK, ADA, and ECG Sampling - Dose Escalation Part (Continued)

Treatment Cycle (C)	Notes	Section Reference	Cycl	e 3 to (	Cycle	4			Cyc	le 5 to	o PD		Treatment Discontin- uation visit	Safety Follow- up visit	Survival Follow- up	Unsched- uled
Day (d)/ Week (wk)			1d	8d	9d	11d	15d	1d	2d	4d	8d	15d	-	30d after last dose	Every 12 wk after last dose	
Visit window			+3d	+1d			+3d	+3d			+3d	+3d		+14d	+7d	
PK SAMPLING		9.5														
Before Infusion (on infusion days)	Optional at Unscheduled visits		Xa	Xb			Xb	Xª					X	X		X
End of infusion (+15 min)			$X^a$	X b			X b	Xª								
End of infusion +2 hr (±15 min)				X b				Xc								
End of infusion +6 hr (+3 hr)				Xb												
24 hr sample post end of infusion	C5 only: PK sample 24±2 hr after end of C5D1 infusion (ie, on C5D2)				Xb				Xc							

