72 hr sample post end of infusion	C5 only: PK sample 72±24 hr after end of C5D1 infusion (ie, on C5D4)					Xb				Xc						
168 hr sample post end of infusion	C5 only: Collect PK sample 168+72 hr after end of C5D1 infusion (ie, on C5D8)										X c					
336 hr sample post end of infusion	C5 only: Collect PK sample 336+72 hr after end of C5D1 infusion (ie, on C5D15)											Xc				
AD A CAMPINE		0.6														
ADA SAMPLING		9.6														
Before Infusion (on infusion days)	Optional at Unscheduled visits		$X^d$					$X^{d}$					X	X		X

Document Number: TMF-34513

Treatment Cycle (C)	Notes	Section Reference	Cycl	e 3 to (	Cycle	4			Сус	ele 5 t	o PD		Treatment Discontin- uation visit	Safety Follow- up visit	Survival Follow- up	Unsched- uled
Day (d)/ Week (wk)			1d	8d	9d	11d	15d	1d	2d	4d	8d	15d	-	30d after last dose	Every 12 wk after last dose	
Visit window			+3d	+1d			+3d	+3d			+3d	+3d		+14d	+7d	
ECGs		9.3.4														
Before Infusion (on infusion days)	Optional at Unscheduled visits; if performed, ECG in triplicate, performed within 20 minutes but at least 2 min apart		Xe													X
End of infusion (+15 min)			Xe													

a. Collect PK samples at C3D1, C4D1, C5D1, C6D1, C7D1, then every 4 cycles thereafter on Day 1.
b. Only collect during C3.
c. Only collect during C5. 

d. Collect ADA samples at C3D1, C5D1, C7D1, then every 4 cycles thereafter on Day 1.
e. Only to be collected for C3D1, not remaining cycles. 

Document Number: TMF-34513

Version: 4.0

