### **4.2 Dose Escalation Part**

The rationale for the starting dose selection is provided in Section 4.6.	

Version: 4.0

The rationale behind implementation of intermediate dose(s) is to mitigate potential AEs (including CRS).

The DLT period will extend from the first dose on C1D1 until 7 days after the first full dose:

The planned doses are:

- a priming dose of 0.3 mg or higher,
- a full dose,
- one, or potentially two, intermediate doses in-between the prime and full dose (if two intermediate doses are used the 1st will be lower than the 2nd). The DLT period will vary, depending on whether one or two intermediate doses are given (see above).

Higher dose levels might be explored depending on accrued data during the escalation part. All doses are fixed doses (not weight adjusted).

The FIH single-subject cohort is planned with a priming dose of 0.3 mg on C1D1, followed by a full dose of 3.0 mg on C1D8 and C1D15.

In the escalation part, the cohort sizes will start with single-subject cohorts. The trigger point to expand a 1-subject cohort into a 3-subject cohort is the observation of any of the following events:

- A grade  $\geq 2$  AE is observed within the DLT period.
- A DLT (see Section 7.1) is observed at any time within the DLT period.

That is, when any of these events occur in a 1-subject cohort, it is expanded by 2 additional subjects. When those subjects have completed their DLT period, the escalation model in Section 4.2.1 is initiated. If the single-subject cohorts reach the maximum dose level (beyond which no escalation is possible), it will be mandatory to expand that cohort size to 3 subjects.

In addition, in the single subject-cohort phase, the next cohort can start only once the DLT period for the previous dose level has been assessed and the next dose level is proposed by the DEC and endorsed by the SC. The DEC will recommend the dose level for the next cohort of subjects to the SC and this will need to be endorsed by the SC prior to using the recommended or higher dose in the next cohort dose level implementation. To supplement routine safety monitoring by the sponsor SC as outlined in this protocol, a DMC will monitor safety data for the trial on a quarterly basis or more frequently as determined by the sponsor. Additional details regarding the DEC, sponsor SC, and the DMC can be found in Section 10.9 and in Section 10.10.

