## 11.6.10 Secondary Endpoint – Pharmacokinetics

PK will be analyzed as described in Section 11.5.8.

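### In cohorts with an intermediate dose, the escalation ECGs stay on C1D1 and C1D8 and miss the first full dose; the expansion 24-hour PK samples miss every full dose

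*Protocol*

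**What the plan says.** **Dosing.** Table 5, footnote f, gives the two v4.0 sequences. With one intermediate dose: "A priming dose on C1D1; an intermediate dose on C1D8; and the first full dose on C1D15". With two: "A priming dose on C1D1; intermediate doses on C1D8 and C1D15; and the first full dose on C2D1". Protocol Section 7.1 describes the same two sequences for the escalation. The first-in-human cohort is different: Section 4.2 has the priming dose "followed by a full dose of 3.0 mg on C1D8 and C1D15".

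**Escalation ECGs (Table 2).** Before infusion and at end of infusion, the instruction is "Triplicate ECGs, performed within 20 minutes but at least 2 min apart". On dosing days in Cycles 1 and 2 the marks are at C1D1 and C1D8 only. The next set is at C3D1, with footnote e: "Only to be collected for C3D1, not remaining cycles". Section 11.5.12.2 plans a categorical analysis of QT/QTc.

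**Expansion ECGs (Table 6).** A single ECG is taken at Screening and at Treatment Discontinuation, with optional unscheduled ones. None is scheduled on a dosing day.

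**Expansion PK (Table 6).** Pre-infusion and end-of-infusion samples are taken on every dosing day of Cycles 1 and 2, then at C3D1, C5D1, C7D1 and every fourth cycle. The 24-hour samples are restricted: "Collect C1D2 and C1D9 PK sample 24 hr ±2 hr after end of D1 and D8 infusion, respectively". Table 10 lists clearance, volume, AUClast, AUCinf, Cmax, Tmax, Ctrough and half-life as secondary endpoints. Section 11.6.10 says "PK will be analyzed as described in Section 11.5.8", and that section uses non-compartmental methods.

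**The concern.** Once an intermediate dose occupies C1D8, an ECG on that day no longer observes the full dose. Table 2 has PK sampling around both possible first full-dose days, C1D15 and C2D1, but its ECG rows have nothing on either. I found no stated reason for keeping Day 8.

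What is at stake is cardiac safety information at the step up to the full dose. The DLT period ends seven days after the first full dose, on Day 21 or Day 28, and the Dose Escalation Committee then reviews the cohort. In these cohorts no scheduled ECG has been taken on the full dose by then. A subject who leaves before Cycle 3 contributes only priming- and intermediate-dose on-dosing ECGs to the QTc analysis. The expansion cannot fill the gap, because it has no ECG on a dosing day.

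In the expansion PK, the denser sampling likewise describes the lower doses, while the full-dose intervals have too few points for several of the listed parameters.

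**Working it through.** No figure in the plan needs reproducing. The check sets dosing days against sampling days.

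**Step 1. Timing of the first full-dose ECG.** Cycles last 21 days, so C3D1 = 1 + 2 × 21 = Day 43.

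| Sequence | First full dose | Full doses before C3D1 | ECGs on first full dose | C3D1 is full dose no. |
|---|---|---|---|---|
| One intermediate | C1D15 | C1D15, C2D1, C2D8, C2D15 = 4 | 0 | 5 |
| Two intermediates | C2D1 | C2D1, C2D8, C2D15 = 3 | 0 | 4 |
| First-in-human | C1D8 | C1D8, C1D15, C2D1, C2D8, C2D15 = 5 | pre- and end-of-infusion sets | 6 |

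Measured from the end of the DLT period, the first full-dose ECG comes 43 − 21 = 22 days later (one intermediate) or 43 − 28 = 15 days later (two).

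**Step 2. Cohorts concerned.** SAP Table 1, full dose divided by the C1D8 dose:

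- 1/3/10: 10/3 = 3.3
- 1/3/30: 30/3 = 10
- 1/5/30: 30/5 = 6
- 1/10/30: 30/10 = 3
- 1/5/30/37.5: 37.5/5 = 7.5
- 1/5/45: 45/5 = 9
- 1/3/60: 60/3 = 20
- 0.3/3/3 and 1/5/5: ratio 1, so the C1D8 ECG is on the full dose

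Seven of nine cohorts are affected, with the C1D8 dose 3 to 20 times below the full dose. The 1/5/30/37.5 mg row prints its last two doses in parentheses under an unexplained asterisk, and SAP Section 1.2 says at most one intermediate dose was used. Without that row the count is six of eight, with the same range.

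**Step 3. Early stoppers.** The documents give no proportion stopping before Cycle 3, so the loss could be anything from none to all. In a cohort of three, one early stop leaves 2 of 3 with a scheduled full-dose ECG, and two leave 1 of 3.

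**Step 4. PK points after the first full dose, up to the next dose.**

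| Part | Post-dose samples | Count |
|---|---|---|
| Escalation (Table 2, C1D15 or C2D1) | end of infusion, +2 h, +6 h, 24 h, 72 h, next pre-dose | 6 |
| Expansion (Table 6, C1D15 or C2D1) | end of infusion, next pre-dose at about 168 h | 2 |
| Expansion, priming and first intermediate | end of infusion, 24 h, next pre-dose | 3 |

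Through Cycle 7 the expansion has pre-infusion and end-of-infusion pairs on 7 full-dose days with one intermediate (C1D15, C2D1, C2D8, C2D15, C3D1, C5D1, C7D1) or 6 with two. It has no 24-hour sample after any full dose. From C3D1 the next dosing day (C3D8, and later C6D1) is not sampled, so those intervals have one post-dose point.

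**Step 5. What two points support.** End of infusion gives Cmax and the next pre-dose gives Ctrough. Assuming that a terminal slope needs about three points, half-life is poorly supported, as are AUCinf, clearance and volume, which depend on it. Adding a 24-hour sample gives end of infusion, 24 h and about 168 h, so only two points follow the peak.

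**The case against.** The best defence is that full-dose QTc is observed at C3D1, before and at the end of infusion. If drug accumulates under weekly dosing, exposure there would be at least that of the first full dose. The documents do not quantify accumulation, but the point has force: sampling a repeated full dose is a legitimate choice, and triplicate unscheduled ECGs are also allowed. What remains is timing and early stoppers, which C3D1 cannot address.

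A reader might infer that full-dose QTc is never observed. That is not supported: C3D1 provides it, and in the 0.3/3/3 and 1/5/5 mg cohorts the C1D8 set is on the full dose.

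A reader might also infer that full-dose PK is not measured. That is wrong for both parts. The escalation profiles the first full dose with six post-dose points and later follows C5D1 to 336 hours; the expansion has full-dose peak and trough. Sparser sampling in an expansion that only further describes PK is a normal two-part design. Section 11.5.8 makes the parameters conditional on available data and allows compartmental modelling, and Section 9.5.1 foresees population PK, again depending on data. This stands, and it reduces the PK point to a mismatch between the listed parameters and the schedule.

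Finally, the practical effect is limited. Enrolment was stopped, no expansion data were collected (SAP Section 2.2), and the abbreviated SAP describes no ECG or PK analysis.

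**Conclusion.** The ECG point holds in its narrow form. In v4.0 cohorts with an intermediate dose there is no scheduled ECG on the first full-dose day. The first one on a full dose is on Day 43, at the fifth or fourth full dose, and subjects who leave before Cycle 3 have none. This applies to 7 of 9 SAP cohorts (6 of 8 without the parenthesised row), assuming the intermediate-dose cohorts followed the v4.0 schedule. It is a gap in early safety information, not an absence of full-dose QTc data.

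The expansion PK point is secondary. Full-dose Cmax and Ctrough are available; half-life, AUCinf, clearance and volume by non-compartmental methods are poorly supported, on the assumption that about three terminal points are needed. It affected no results.

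**What to change.** **Table 2.** Move the C1D8 pre-infusion and end-of-infusion triplicate ECGs to the day of the first full dose: C1D15, or C2D1 where two intermediate doses are given. Both are existing dosing visits with pre-infusion and end-of-infusion PK draws, and the number of ECGs is unchanged. The cost is the ECG set at the intermediate dose. Cohorts whose full dose falls on C1D8 keep the present days.

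**Table 6.** Move the C1D9 24-hour sample to C1D16, or to C2D2 with two intermediate doses; Table 5 already has those visits. The cost is the 24-hour sample after the intermediate dose. The biomarker tables are not shown, and the amendment summary says cytokine sampling was aligned with PK, so check whether a cytokine draw is tied to C1D9 before moving it.

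**Table 10 and Section 11.6.10.** The moved sample alone would not rescue the terminal-phase parameters. Limit the expansion's full-dose non-compartmental parameters to Cmax and Ctrough, and take the remaining ones from the population PK analysis in Section 9.5.1.
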